2.10.1.1 Adverse events of special interest / grouping of AEs

The number (%) of patients with adverse events of special interest (AESI) will be summarized by Standardized MedDRA Query and PT. A listing will also be provided.

A Case Retrieval Sheet (CRS) with the exact composition of the AE groupings is to be used to map reported AEs to the AESI groupings. This file may be updated (i.e. it is a living document) based on review of accumulating trial data, and therefore the groupings are also subject to potential change. The most up-to-date version of the CRS will be used at the time of the analysis.

The number and percentage of patients having any AESI, having an AESI in each SOC and having each individual AE (PT) will be presented.

The number and percentage of patients for AESI type along with incidence rate per patient and per 1000 injection will be provided. Incidence rate per patient is defined as number of patients in AESI type/total number of patients in safety analysis set and incidence rate per 1000 injection is define as (number of occurrence of AESI type/total number of injections)*1000.

The number and type of AESI will be plotted according to the time after last brolucizumab injection and time since first brolucizumab injection.

Summary statistics for change from baseline in BCVA after end date of AESI will be provided for each AESI type and change from baseline in BCVA will be plotted overall and for each type of AESI.

Patients demographics, baseline characteristics and medical history will be provided for AESI patient with safety set.

2.10.2 Deaths

A separate summary of deaths including on-treatment and post-treatment deaths will be provided.

All deaths in the clinical database will be listed with the investigator-reported principal cause. Deaths occurring after the first dose of study treatment until 30 days after the date of last

treatment will be summarized. In addition, deaths occurring after the first dose of study treatment until the date of last treatment will also be summarized.

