12.5.5 Safety endpoints

The Safety Set will be used for all safety analyses.

The secondary safety endpoint of this study is as follows:

- Incidence of AEs (serious and non serious) reported in patients treated with brolucizumab.

Safety summaries (tables, figures) include only data from the on-treatment period with the exception of Baseline data, which will also be summarized where appropriate (e.g. change from Baseline summaries). In addition, a separate summary for death including on treatment and post treatment deaths will be provided. In particular, summary tables for adverse events of special interest (AESIs) will summarize only on-treatment events, with a start date during the on-treatment period (treatment-emergent AEs).

The on-treatment period lasts from the date of first administration of IVT injection of study treatment to 30 days after the date of the last actual administration of IVT injection of study treatment.

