Percent change from Baseline: The percent change from baseline will be calculated as below: $((\text{post-baseline value} - \text{Baseline value}) / \text{Baseline value}) * 100$.

Proportion: A proportion refers to the fraction of the total that possesses a certain attribute. In this study attribute is disease free activity.

Disease control: When patients have no disease activity after taking study treatment then patient will be consider as disease control.

On-treatment period: The on-treatment period lasts from the date of first administration of study treatment to 30 days after the date of the last actual administration of any study treatment.

Treatment duration: The maximum planned duration of treatment for each patient is 44 to 46 weeks in accordance with the designated treatment regimen. Discontinuation of study treatment for a patient occurs when study treatment is stopped earlier than the protocol planned duration and can be initiated by either the patient or the investigator.

Treatment discontinuation: When patients discontinue study treatment but continue in the study, the efficacy data will be used at the time the patient stopped study treatment.

Last interval: The last treatment interval (defined by the investigator) before Week 48.

Maximum interval: The longest interval of treatment reached by the patient over the study period.

Event for no disease activity: When patients will be with no disease status as per investigator decision after last dose in initiation phase then the patients will consider as event for no disease activity. If patients with active disease status or early discontinue then patients will be considered as censored for disease activity.

Dry retina: Absence of fluid (IRF/SRF/ sub-RPE) will be considered as dry retina.

Event for dry retina: When patients have absence of fluid then it will be considered as an event of dry retina. If patients have a presence of fluid before/at EOS or early discontinuation then will be censored.

[figure not shown]
Study eye and fellow eye: The investigator selects the eye with the worse BCVA at Screening as the study eye if both eyes are eligible as per the inclusion and exclusion criteria, unless the investigator deems as a study eye more appropriate to select the eye with better BCVA, based on medical reasons or local ethical requirements. If both eyes are eligible as per the inclusion and exclusion criteria, then it is recommended to select the right eye as the study eye.

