2.1.1 General definitions

Study treatment: This is a single-arm study and all patients will be treated with brolucizumab 6 mg. Three loading injections (at Screening/Baseline/Day 1, Week 4 and Week 8), followed by a Treat-to-Control (TtC) regimen phase based on disease activity from Week 8 up to Week 44/46 (according to the treatment regimen). The investigator can individualize treatment intervals depending on disease activity, to adjust patient's injection regimen.

Study treatment start and end date: Study treatment start date is defined as the first date study treatment is administered and recorded on the Treatment Administration Record (DAR) Electronic Case Report Form (eCRF) page. Similarly, study treatment end date is defined as the last date of study treatment is administered and recorded on the Study Treatment Completion eCRF page.

Generally, study Day 1 is considered as the day of inclusion of the patient. However in this study, treatment is intended to be administered on the same day or if this is not possible, within 3 days after the day of inclusion of the patient.

Study day will be calculated as ((event date – study treatment start date) + 1 day) for events that occurred on or after study treatment start date (e.g. visit, AEs). For events prior to study treatment start date (e.g. time since diagnosis), study day will be negative and calculated as (event date – study treatment start date).

Baseline and post-baseline: Baseline value refers to the value of the last non-missing measurement collected prior to administration of the first dose of study treatment (Screening or Baseline visit). [REDACTED]

A “post-baseline” value refers to a measurement taken after the first dose of study treatment. When assessments and treatments take place on the same day, treatment must occur after completion of the efficacy assessments and pre-injection safety measures (tonometry, slit lamp [REDACTED]). If study visit assessments and the corresponding treatment occur on separate days, a repeat safety check-up will be performed prior to treatment of the eye and results documented in the source documents. More post-baseline safety measurements will be recorded in source document; visit window will be applied to OCT and IVT visits.

Change from Baseline: The difference of measure between post-baseline and Baseline is called change from Baseline.

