Percent change from Baseline: The percent change from baseline will be calculated as below: $((\text{post-baseline value} - \text{Baseline value}) / \text{Baseline value}) * 100$.

Proportion: A proportion refers to the fraction of the total that possesses a certain attribute. In this study attribute is disease free activity.

Disease control: When patients will have no disease activity after taking study treatment then patient will be consider as disease control.

On-treatment period: The on-treatment period lasts from the date of first administration of study treatment to 28 days after the date of the last actual administration of any study treatment.

Treatment duration: The maximum planned duration of treatment for each patient is 44 to 46 weeks in accordance with the designated treatment regimen. Discontinuation of study treatment for a patient occurs when study treatment is stopped earlier than the protocol planned duration and can be initiated by either the patient or the investigator.

Treatment discontinuation: When patients discontinue study treatment but continue in the study, the efficacy data will be used at the time the patient stopped study treatment.

Last interval: The last treatment interval (defined by the investigator) before Week 48.

Maximum interval: The longest interval of treatment reached by the patient over the study period.

Event for no disease activity: When patients will be with no disease status as per investigator decision after last dose in initiation phase then the patients will consider as event for no disease activity. If patients with active disease status or early discontinue then patients will be considered as censored for disease activity.

Dry retina: Absence of fluid (IRF/SRF/ sub-RPE) will be considered as dry retina.

Event for dry retina: When patients have absence of fluid then it will be considered as an event of dry retina. If patients have a presence of fluid before/at EOS or early discontinuation then will be censored.

Study eye and fellow eye: The Investigator selects the eye with the worse BCVA at Screening as the study eye if both eyes are eligible as per the inclusion and exclusion criteria, unless the investigator deems as a study eye more appropriate to select the eye with better BCVA, based

on medical reasons or local ethical requirements. If both eyes are eligible as per the inclusion and exclusion criteria, then it is recommended to select the right eye as the study eye.

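### The second death summary, from first dose to date of last treatment, is empty apart from same-day or imputed-date deaths; the interim SAP's 28-day on-treatment period also conflicts with the 30 days used elsewhere

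*SAP*

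**What the plan says.** SAP 2.9.2 and interim SAP 2.10.2 use the same wording and plan four outputs.

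1. A general summary: "A separate summary of deaths including on-treatment and post-treatment deaths will be provided". Protocol 12.5.5 asks for the same thing: "a separate summary for death including on treatment and post treatment deaths will be provided".
2. A listing: "All deaths in the clinical database will be listed with the investigator-reported principal cause".
3. A first windowed summary: "Deaths occurring after the first dose of study treatment until 30 days after the date of last" treatment.
4. A second windowed summary: "deaths occurring after the first dose of study treatment until the date of last treatment will also be summarized".

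Both SAPs fix the meaning of the last treatment date in section 2.1.1: "study treatment end date is defined as the last date of study treatment is administered".

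The on-treatment period, which selects events for the adverse event tables, has several definitions. The final SAP (2.1.1) runs it "to 30 days after the date of the last actual administration of any study treatment". The interim SAP (2.1.1) has: "The on-treatment period lasts from the date of first administration of study treatment to 28 days after the date of the last actual administration". Protocol 12.5.5 ends it 30 days after the last actual injection. Protocol 12.5.5.1 ends it at 30 days or at end of study, whichever is later. Section 4 of both SAPs declares no change to the protocol's analyses.

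**The concern.** A window that closes on the date of last treatment makes sense for a drug taken daily, where a patient can die during a course. Here the last treatment is the last injection the patient lived to receive, so the window closes before almost any death can enter it. A report that prints zero in that row invites the reading that nobody died on treatment, although the row would print zero whatever the drug did.

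The other explicit window closes at day 30. The term post-treatment has no start or end day of its own, so a programmer working from the two stated windows would tabulate no death after day 30. This programme was amended repeatedly for safety signals and follows patients for months after early discontinuation, so those deaths should have a defined place in a table.

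The 28-day period in the interim SAP is a separate defect. A fatal event starting and ending on day 29 or 30 after the last injection would fall inside the 30-day death window but be missing from the interim adverse event and SAE tables.

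**Working it through.** The plan states no number of deaths, so there is no figure to reproduce. The check is on the logic of the windows and on day counts.

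**Second death window.** Let L be the date of the last actual injection and D the date of death. Injections are given only to living patients, so L ≤ D. The window requires D ≤ L. Both hold only if D = L, a death on the injection day, assuming the window includes its last day. One artefact can add cases: section 5.1.1 of both SAPs replaces a missing dose end date by the end-of-treatment date, and moves some partial dates to the end of the month or year. An imputed L can therefore fall on or after D.

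**Who can die beyond day 30.** Three groups follow from the protocol.

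*Patients between injections.* After Week 8 the intervals are 8, 12 or 16 weeks (Protocol 6.7.2.2).

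| Interval | Days | Covered by 30 days | Days beyond 30 |
|---|---|---|---|
| 8 weeks | 56 | 30/56 = 54% | 26 |
| 12 weeks | 84 | 30/84 = 36% | 54 |
| 16 weeks | 112 | 30/112 = 27% | 82 |

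*Patients who complete the study.* Treatment can end at Week 38, 40, 42, 44 or 46 (Protocol, Figure 3-1, footnote a). On nominal dates, days beyond 30 are (end-of-study week − last injection week) × 7 − 30, floored at zero:
- Week 38: 70 − 30 = 40 days
- Week 40: 56 − 30 = 26 days
- Week 42: 42 − 30 = 12 days
- Week 44 (end of study at Week 48) and Week 46 (end of study at Week 50): 28 days of follow-up, so none

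*Patients who stop treatment early.* They are followed at least to Week 48 (Protocol 9.1.1). With 48 × 7 = 336 days:
- Last injection Week 8: 336 − 56 − 30 = 250 days = 35.7 weeks
- Last injection Week 14: 336 − 98 − 30 = 208 days = 29.7 weeks
- Last injection Week 16: 336 − 112 − 30 = 194 days = 27.7 weeks

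**Illustration.** The documents give no distribution of death times. Assume that deaths are spread evenly over days 1 to 336, that no patient stops early, and that injections fall on days 0, 28, 56 and 112 and then at one fixed interval, the last no later than day 308. Counting days gives:

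| Interval after Week 16 | Before last injection | Same day | Days 1–30 | Beyond day 30 |
|---|---|---|---|---|
| 8 weeks | 0 | 6/336 = 1.8% | 204/336 = 60.7% | 126/336 = 37.5% |
| 12 weeks | 0 | 5/336 = 1.5% | 174/336 = 51.8% | 157/336 = 46.7% |
| 16 weeks | 0 | 4/336 = 1.2% | 144/336 = 42.9% | 188/336 = 56.0% |

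An equal mix of the three puts 157/336, about 47%, beyond day 30. The protocol extends intervals by 4 weeks at a time, so a fixed 12- or 16-week interval from Week 16 is a simplification. The zero in the first column does not depend on these assumptions.

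**28 against 30 days.** The period runs to the last actual injection plus the tail, so events between two injections are counted under either rule. The loss is days 29 and 30 after each patient's last injection: at most 2 × 295 = 590 patient-days if the planned number is treated. Protocol 10.1.1 collects adverse events to 30 days after the last injection, so the data exist.

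**The case against.** The strongest reply is that nothing is lost. Both sections open by promising a summary that covers post-treatment deaths, every death is listed with its cause, and the two windowed counts are further outputs rather than the definition of the first. This is largely right. A reader might infer that late deaths would be visible only in a listing, but the opening sentence says otherwise. What remains is that post-treatment is defined only as the complement of an on-treatment period that itself has conflicting ends, and that the explicit windows stop by day 30.

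A reader might also infer that late deaths can come only from patients stopped early, for example for inflammation or vascular occlusion. The documents do not support this either. Patients still on schedule spend 26 to 82 days of each interval beyond day 30, and completers last injected at Week 38 to 42 have 12 to 40 such days.

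Third, the window is not strictly zero, because same-day deaths and imputed dates can enter it. That stands, but neither makes the row informative.

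Finally, SAP 2.15 reports the interim analysis as already performed, and the final SAP uses 30 days for both periods. The 28-day conflict is therefore confined to interim output. It still contradicts both protocol definitions, and section 4 of the interim SAP does not declare it.

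**Conclusion.** The point holds in limited form. The second death summary is uninformative by definition. That conclusion rests only on reading the date of last treatment as the last actual injection, which both SAPs state. Neither explicit window reaches past day 30, although follow-up beyond day 30 exists in all three groups above and reaches 27.7 to 35.7 weeks for patients last injected at Week 16 to Week 8. The share of deaths beyond day 30, 37.5% to 56.0% in the illustration, depends on assumed schedules and evenly spread deaths and is not a forecast.

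The interim SAP's 28 days is a plain conflict with the protocol, with the final SAP and with its own death window. It affects at most two days per patient.

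The consequences stop at descriptive safety tables. No efficacy result changes, and no death is omitted from the plan.

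**What to change.** 1. In SAP 2.9.2, replace the second window with deaths after the end of the on-treatment period up to last study contact. Show on-treatment, post-treatment and total deaths in one table.
2. Reconcile Protocol 12.5.5 (30 days) with 12.5.5.1 (30 days or end of study, whichever is later), and use the one resulting cut-off for adverse event, SAE and death tables. This comes first: under the later-of rule a death on day 60 before end of study counts as on-treatment, so the choice decides what the post-treatment row contains.
3. Change the 28 days in interim SAP 2.1.1 to that cut-off and make the same death-table change in interim SAP 2.10.2. Apply both to any reissued interim output, and record the difference for output already produced.

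The cost is a sentence or two in each SAP, one table row, and a protocol clarification. No new data are needed.

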2.10.3 Laboratory data

Not applicable.

2.10.4 Other safety data

Not applicable.

2.10.4.1 ECG and cardiac imaging data

Not applicable.

2.10.4.2 Vital signs

Vital signs will include blood pressure and pulse rate measurements.

All vital signs data will be listed by patient, and visit, and if ranges are available, abnormalities will be flagged. Abnormal values are marked in [Section 5.3](#). All data, including data from unscheduled visits, will be considered when identifying abnormal values. Analysis of vital sign measurements using summary statistics for the change from Baseline for each post-baseline visit will be performed. These descriptive summaries will be presented by vital sign. Change from Baseline will only be summarized for patients with both Baseline and post-baseline values.

2.11 Pharmacokinetic endpoints

Not applicable.

2.12 PD and PK/PD analyses

Not applicable.

2.13 Patient questionnaire

Not applicable for IA.

2.14 Biomarkers

Not applicable

2.15 Other Exploratory analyses

Not applicable

3 Sample size calculation

The sample size calculation is based on the hypothesis of 25% to 35% of patients with no disease activity at Week 16. The sample size analyses were performed before the urgent safety measures were introduced.

Table 3-1 Confidence intervals for proportions (2 sided)

Confidence level	Sample size (N)	Expected proportion	Target distance from proportion to limit
0.950	250	0.25	0.054
0.950	300	0.25	0.049
0.950	325	0.25	0.047
0.950	400	0.25	0.042
0.950	250	0.30	0.057
0.950	300	0.30	0.052
0.950	325	0.30	0.050
0.950	400	0.30	0.045
0.950	250	0.35	0.059
0.950	300	0.35	0.054
0.950	325	0.35	0.052
0.950	400	0.35	0.047

A sample size of 250 to 400 patients produces a 2-sided 95% confidence interval with a distance from the proportion to the limits ranges from 0.042 to 0.059 when the estimated proportion varies from 0.25 to 0.35 (nQuery Advisor version 7.0).

In the HAWK and HARRIER studies, the proportion of naïve nAMD patients treated with brolucizumab who had disease activity at Week 16 was 30% less than for patients treated by aflibercept.

To determine a similar 30% proportion of patients with no disease activity at Week 16 in this pretreated study with a precision of 5% and alpha 5% (2-sided 95% confidence interval of width 11%), a total of 265 patients have to be observed in this study.

Considering a dropout rate of 10%, a total of 295 patients will be included.

4 Change to protocol specified analyses

Not applicable

5 Appendix

5.1 Imputation rules

5.1.1 Study treatment

The following rules should be used for the imputation of the dose end date for a given study treatment component:

Scenario 1

If the date of last IVT is completely missing and there is no end of treatment (EOT) page and no death date, the patient is considered as on-going.

The patient should be treated as on-going and the cut-off date should be used as the last dosing date.

Scenario 2

If the dose end date is completely or partially missing and the EOT page is available:

- Case 1: The dose end date is completely missing and the EOT completion date is complete, then this latter date should be used.
- Case 2: Only year (YYYY) of the dose end date is available and YYYY < the year of EOT date, then use 31DECYYYY.
- Case 3: Only year (YYYY) of the dose end date is available and YYYY = the year of EOT date, then use EOT date.
- Case 4: Both year (YYYY) and month (MMM) are available for dose end date and YYYY = the year of EOT date and MMM < the month of EOT date, then use last day of the Month (MMM)

All other cases should be considered as a data issue and the statistician should contact the data manager of the study.

After imputation, compare the imputed date with start date of treatment.

If the imputed date is < start date of treatment, then use the treatment start date.

Otherwise, use the imputed date

Patients with missing start dates are to be considered missing for all study treatment component related calculations and no imputation will be made. If start date is missing then end-date should not be imputed.

5.1.2 AE date imputation

AE date imputation is based only on a comparison of the partial AE start date to the treatment start date as mentioned in the below.

1. If the AE start date year value is missing, the date uncertainty is too high to impute a rational date. Therefore, if the AE year value is missing, the imputed AE start date is set to NULL.
2. If the AE start date year value is less than the treatment start date year value, the AE started before treatment. Therefore:
 - a. If the AE year is less than the treatment year and the AE month is missing, the imputed AE start date is set to the mid-year point (01JulYYYY).
 - b. Else if the AE year is less than the treatment year and the AE month is not missing, the imputed AE start date is set to the mid-month point (15MONYYYY).
3. If the AE start date year value is greater than the treatment start date year value, the AE started after treatment. Therefore:
 - a. If the AE year is greater than the treatment year and the AE month is missing, the imputed AE start date is set to the year start point (01JanYYYY).

- b. Else if the AE year is greater than the treatment year and the AE month is not missing, the imputed AE start date is set to the month start point (01MONYYYY).
- 4. If the AE start date year value is equal to the treatment start date year value:
 - a. And the AE month is missing or the AE month is equal to the treatment start month, the imputed AE start date is set to one day after treatment start.
 - b. Else if the AE month is less than the treatment start month, the imputed AE start date is set to the mid-month point (15MONYYYY).
 - c. Else if the AE month is greater than the treatment start month, the imputed AE start date is set to the start month point (01MONYYYY).

	MON	MON < CFM	MON = CFM	MON > CFM
	MISSING			
YYYY MISSING	NULL	NULL	NULL	NULL
	Uncertain	Uncertain	Uncertain	Uncertain
YYYY < CFY	(D) = 01JULYYYY	(C) = 15MONYYYY	(C) = 15MONYYYY	(C) = 15MONYYYY
	Before Treatment Start	Before Treatment Start	Before Treatment Start	Before Treatment Start
YYYY = CFY	(B) = TRTSTD+1	(C) = 15MONYYYY	(A) = TRTSTD+1	(A) = 01MONYYYY
	Uncertain	Before Treatment Start	Uncertain	After Treatment Start
YYYY > CFY	(E) = 01JANYYYY	(A) = 01MONYYYY	(A) = 01MONYYYY	(A) = 01MONYYYY
	After Treatment Start	After Treatment Start	After Treatment Start	After Treatment Start
Before Treatment Start	Partial indicates date prior to Treatment Start Date			
After Treatment Start	Partial indicates date after Treatment Start Date			
Uncertain	Partial insufficient to determine relationship to Treatment Start Date			
LEGEND:				
(A)	MAX(01MONYYYY, TRTSTD+1)			
(B)	TRTSTD+1			
(C)	15MONYYYY			
(D)	01JULYYYY			
(E)	01JANYYYY			

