5.3 Confirmed SRC event

List of confirmed SRC event will be provided by study team. Trial programmer will derive below variable to performed the related analysis.

- a) SRC start and SRC event date
- b) Number of IVT injection prior to start of AESI event confirmed by SRC
- c) Duration(day) since last IVT injection to start of AESI event confirmed by SRC

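### Partial adverse-event dates are imputed against the first injection only, so a partly dated AESI after a later injection can be shown at the wrong lag in the AESI timing plots

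*SAP*

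**What the plan says.** The SAP file holds a final SAP and an interim SAP. The imputation rule in section 5.1.2 is the same in both: "AE date imputation is based only on a comparison of the partial AE start date to the treatment start date". Section 2.1.1 of both fixes the reference date: "Study treatment start date is defined as the first date study treatment is administered".

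Three cases matter here:

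- **Day missing, month after the first-dose month (rules 3b and 4c):** the onset becomes the first day of the reported month.
- **Month missing in the first-dose year, or month equal to the first-dose month (rule 4a):** "the imputed AE start date is set to one day after treatment start".
- **Floor (legend A under the table):** the imputed date may not be earlier than the day after the first injection. No rule or floor refers to a second or later injection.

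The onset date is then used for timing. Final SAP 2.9.1.1 and interim SAP 2.10.1.1 both state: "The number and type of AESI will be plotted according to the time after last brolucizumab injection". Both also plot by time since the first injection. Interim SAP 5.3 alone derives, for AESIs confirmed by the safety review committee (SRC), the number of earlier injections and "Duration(day) since last IVT injection to start of AESI event confirmed by SRC". Neither SAP gives a separate date rule for AESIs.

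The opening text of the safety analyses (final SAP 2.9, interim SAP 2.10) says that missing safety data will not be imputed. Neither SAP reconciles this with 5.1.2.

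**The concern.** Rule 5.1.2 suits the question of whether an event began before or after treatment started, because uncertain dates default to after the first dose. A plot of lag from the last injection asks something else, and its reference is the most recent injection. Every patient is due injections at Day 1, Week 4 and Week 8, with more to follow (protocol 6.7.2), so the first-dose date does not give enough information to place an event.

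Intraocular inflammation, with retinal vasculitis or vascular occlusion, drove the urgent safety measures and several protocol amendments. A reader will use the plot to see how soon after a dose these events arise. If AESIs are few, one or two misplaced points can change that picture. The rule can turn a short lag into a long one or, under rule 4a, a late event into one on the day after the first dose.

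**Working it through.** There is no plan figure to reproduce. The check applies the written rules to known dates.

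**Worked cases.** Take injections on 15 March, 12 April, 10 May and 5 July 2021 (Day 1, Weeks 4, 8 and 16), with true onset 8 days after an injection.

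| True onset | Reported as | Imputed | Injections before onset: true / imputed | Lag in days: true / imputed |
|---|---|---|---|---|
| 20 April | April | 1 April | 2 / 1 | 8 / 17 |
| 18 May | May | 1 May | 3 / 2 | 8 / 19 |
| 13 July | July | 1 July | 4 / 3 | 8 / 52 |
| 13 July | year only | 16 March | 4 / 1 | 8 / 1 |

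**How often, for day-missing events after a second or later injection.** Assumptions: the injection day D is uniform on 1 to 30 in a 30-day month, and the true lag l is uniform on 1 to L days. The event is tied to the previous dose when onset falls in the injection's own month (D + l ≤ 30) and D is at least 2. For each l up to 28 that leaves 29 − l values of D, so the share is Σ(29 − l) / (30L):

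- L = 14: 301 / 420 = 72%
- L = 28: 406 / 840 = 48%
- L = 56: 406 / 1680 = 24%

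**Recorded lag when tied to the wrong dose (L = 28).** Over these 406 combinations the mean of l is 10 and the mean of D − 1 is 10. The recorded lag is the preceding interval minus (D − 1). Its mean is 28 − 10 = 18 days after a 4-week interval, 56 − 10 = 46 after 8 weeks and 84 − 10 = 74 after 12 weeks, against a true mean of 10.

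**Check on calendar dates.** With every 2021 start date and injections at days 0, 28, 56 and 112, the share misplaced after injection 2, 3 or 4 is 87% at a true lag of 3 days, 74% at 7, 51% at 14, 28% at 21 and 8% at 27. After injection 1 it is 0%, because the floor prevents it. The lag is still shortened there: a true 7 days becomes 1.7 on average.

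**An alternative rule.** One could impute the later of the first of the month and the day after the last injection in that month. On the same calendar:

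| Preceding and following interval | True lag, uniform | Correct dose: current rule | Correct dose: alternative |
|---|---|---|---|
| 4 weeks | 1 to 27 days | 49% | 46% |
| 4 weeks | 1 to 14 days | 28% | 67% |
| 8 weeks | 1 to 55 days | 75% | 73% |

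The alternative helps only if onset is early relative to the interval. It also records a lag of exactly 1 day for every event whose reported month contains an injection.

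**The case against.** The strongest reply is that the rule does its usual job, and that the documents tie less to it than a reader might infer. Most of that stands.

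- **Injection count.** A reader might infer that it will be wrong. It is derived only in interim SAP 5.3, from a list of confirmed events supplied by the study team, with SRC dates as a separate item. The text does not say that the imputed AE date is used, so an error there is conditional.
- **Both SAPs.** The imputation rule and the plots are common to both. The injection count, the derived lag variable and the AE tables split at 16 weeks (interim SAP 2.10.1) are not in the final SAP, where only the plots are exposed.
- **All day-missing AESIs.** The 48% does not apply to all of them. It covers events after a second or later injection.
- **Size of the shift.** It is not always most of an interval. After a 4-week interval the mean goes from 10 to 18 days. Only after 8 or 12 weeks is the increase large (36 and 64 days).
- **Exposure.** The protocol asks for AE start and end dates as far as possible (10.1.1), queries missing values (11.2) and wants patients with symptoms examined at once (8.4.3). Partial AESI dates may be rare.
- **Role of the output.** The safety endpoint is AE incidence, and the timing plots are descriptive.

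The statement that missing safety data are not imputed could mean that imputed dates never reach the plots. It does not settle the matter, because 5.1.2 imputes AE dates without limiting their use.

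**Conclusion.** The point holds as a minor one. If the 5.1.2 dates feed the AESI plots, a day-missing AESI after a second or later injection is shown against the wrong dose in about half of cases with onset uniform over 28 days, and more often if onset is earlier. A month-missing AESI in the first-dose year is always shown one day after the first injection. Events after the first injection stay with the right dose, although their lag can be shortened.

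The shares rest on assumed onset distributions and on injection days spread evenly over the month. The documents do not give the number of partly dated AESIs; if there are none, nothing changes. A reader might infer that AESI incidence is distorted. The documents do not support that: the patient counts and the rates per 1000 injections (final SAP 2.9.1.1, interim SAP 2.10.1.1) do not use the lag from injection to onset.

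**What to change.** State in 5.1.2 of both SAPs that imputed start dates serve treatment-emergent classification only. For the AESI timing outputs (final SAP 2.9.1.1, interim SAP 2.10.1.1 and 5.3):

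- **Day missing:** show the earliest and latest possible lag and injection count, given the patient's actual injection dates. For an onset reported as May in the example above, these are 2 injections with a lag of 19 to 27 days (1 to 9 May), or 3 injections with a lag of 0 to 21 days (10 to 31 May). The true 8 days lies inside the second range.
- **Month missing:** show lag and count as unknown.
- **Both:** report how many AESIs fall in each group.

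Say in interim SAP 5.3 which date the SRC-confirmed derivations use. Reconcile 5.1.2 with the no-imputation statement in final SAP 2.9 and interim SAP 2.10.

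The cost is a few sentences and a few lines of code. The downside is that some events appear as ranges or in a footnote instead of as single points.
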